5.4. Study Blinding

The Sponsor or designee, the Investigator, study-site personnel, and the patient will be blinded to treatment assignment. The integrity of the clinical study will be maintained by observing the treatment blind. If knowledge of a patient's treatment assignment is required for the patient's clinical care and/or safety, the Investigator should consult with the Sponsor's medical monitor prior to breaking the blind.

5.4.1. Unblinding Treatment Assignment

Unblinding the treatment assignment of a patient may only be performed in emergencies where knowledge of the patient's treatment assignment is essential for management of the patient's medical care. Unblinding the treatment assignment by the investigator under any other circumstances will be considered a protocol violation. The investigator should make every effort to contact the Sponsor or designee prior to unblinding a patient's treatment assignment. In the event of any unblinding, emergency or accidental, the sponsor must be notified within 1 business day.

Unblinding will occur using the EDC. The Investigator must record the date and time the blind was broken, the names of the personnel involved, and the reason that treatment assignment information was required. The date and time that the Sponsor or designee was notified will also be recorded.

5.5. Study Drug Administration

Study drug will be administered to all patients in the clinic by designated and trained site staff.

5.5.1. Instructions for Administration in the Clinic

Syringes should be at room temperature prior to injection (refer to the applicable Instructions for Use provided by the sponsor).

5.6. Study Drug Accountability

The Investigator must keep an accurate record of the number of cartons received, the study drug dispensed/used, and those returned to the Sponsor or designee. The Sponsor or designee will provide forms to facilitate inventory control. All study-drug accountability forms and treatment logs must be retained in the Investigator's permanent study file, and these records must be available for inspection at any time by the Sponsor, its designees, or by regulatory agencies.

The study monitor will perform drug accountability for all study drug at the site, and will assist in returning all used, unused, and expired materials, to the Sponsor/designees, or destroy it according to the study site's standard operating procedure, if accepted by the Sponsor.

6. CONCOMITANT MEDICATIONS AND PROCEDURES

All medications (including over-the-counter drugs, vitamins, and antacids) and over-the-counter emollient(s) taken/used at screening and throughout the study must be recorded. Patients should be instructed to consult with the Investigator prior to initiating any new medication (either self-administered non-prescription drugs or prescription therapy prescribed by another physician) while participating in the study. The Investigator is expected to examine the acceptability of all concomitant medications, topical preparations, and dietary supplements taken by patients participating in the trial.

- Medication entries should be specific to product name (if a combination drug product) and spelled correctly.
- The brand and specific product name for any over-the-counter emollient(s) should be noted and spelled correctly.
- Information on the dose, unit, frequency, route of administration, start date, discontinuation date, indication, and reason for use will be recorded.
- The use of any concomitant medication must relate to an AE listed on the AE electronic case report form (eCRF) or the patient's medical history unless it is a supplement or used as preventative care.

6.1. Permitted and Prohibited Treatments and Procedures

The use of concomitant medications for other medical conditions (e.g., hypertension, diabetes, acute infections) is permitted during this study. Inhaled corticosteroids and bronchodilators to control asthma are permitted.

The introduction of medications or therapies for other medical conditions known to affect AD (e.g. systemic corticosteroids, mycophenolate-mofetil, IFN- γ , Janus kinase inhibitors, TCI, cyclosporine, azathioprine, methotrexate, phototherapy, or photochemotherapy, phosphodiesterase-4 inhibitors such as crisaborole) are not permitted during the study. The use of systemic corticosteroids for the treatment of AD is prohibited and requires permanent discontinuation of Investigational Product. If used for treatment of AEs (for example, worsening of existing condition, such as asthma exacerbation), it will be treated as rescue medication as per the Section 6.4 .

Acute infections can be treated with systemic antibiotics, use of which must be recorded in the eCRF. However, chronic treatment with systemic antibiotics is not permitted.

The use of a tanning booth/parlor is not permitted during the trial.

Cannabinoid treatments for AD are prohibited.

Planned or anticipated major medical procedures or surgeries should be avoided during the trial.

See Section 6.4 for details on approved rescue medications and timing of use.

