6.3. Topical Treatment for Atopic Dermatitis

All patients will be instructed to use TCS for AD symptoms starting at the Baseline visit (Day 1).

Patients may taper or stop TCS use, as needed. If AD lesions return or a patient experiences a flare, TCS treatment may be resumed at the patient's discretion.

Low-potency TCS or topical calcineurin inhibitors (TCI) may be used for sensitive areas only, i.e., face, neck, intertriginous and genital areas.

A mid-potency TCS, triamcinolone acetonide 0.1% cream, and a low-potency TCS, hydrocortisone 1% cream (for use on sensitive skin areas) will be provided by the Sponsor or clinical site for use in this trial. Patients are to be instructed to return all used and unused TCS medication (tubes) to the study site for accountability purposes.

The Investigator must keep an accurate record of the number of tubes received, dispensed/used, and those returned to the Sponsor or designee. The Sponsor or designee will provide forms to facilitate inventory control. All accountability forms and treatment logs must be retained in the Investigator's permanent study file, and these records must be available for inspection at any time by the Sponsor, its designees, or by regulatory agencies.

The study monitor will perform accountability for all TCS tubes at the site, and will assist in returning all used, unused, and expired materials, to the Sponsor/designees, or destroy it according to the study site's standard operating procedure, if accepted by the Sponsor.

All TCS and TCI use will be recorded daily by the patient using an electronic diary.

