6.4. Rescue Treatment for Atopic Dermatitis

The goal of this Phase 3 study is to demonstrate the efficacy and safety of lebrikizumab when used in combination with TCS for AD. However, add on rescue therapies may be needed, if the patient experiences clinical worsening of symptoms that are intolerable.

If medically necessary (i.e., to control intolerable AD symptoms), high potency TCS or systemic treatments (e.g., oral corticosteroids, phototherapy, cyclosporin, etc.) may be used. Study drug must be discontinued for patients receiving systemic rescue treatment. Patients should continue to attend all study visits and be assessed for safety and efficacy according to the schedule of events, even if rescue medication is initiated.

Patients using topical or systemic rescue medication who complete the study through Week 16 will be eligible to continue to a separate long-term extension study after the Week 16 visit has been completed.

All rescue treatment usage must be captured in the eCRF.

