
**Objectives and Endpoints****Other Efficacy Endpoints**

- Percentage change from Baseline to Week 16 in SCORAD
- Change from Baseline in BSA by visit
- Percentage of patients who respond “Strongly Agree” or “Agree” for each item of the modified SQAAQ by data collection sequence
- Proportion of TCS/TCI-free days from Baseline to Week 16
- Time (days) to TCS/TCI-free use from Baseline to Week 16
- Percentage of patients rescued by visit

Abbreviations: ACQ-5 = Asthma Control Questionnaire 5-item version; AD = atopic dermatitis; BSA = body surface area; CDLQI = Children’s Dermatology Life Quality Index; DLQI = Dermatology Life Quality Index; EASI = Eczema Area and Severity Index; EQ-5D = European Quality of Life–5 Dimensions–5 Levels; EMA = European Medicines Agency; FDA = Food and Drug Administration; IGA = Investigator Global Assessment; NRS = Numeric Rating Scale; PK = pharmacokinetic; POEM = Patient-Oriented Eczema Measure; PROMIS = Patient-Reported Outcomes Measurement Information System; SCORAD = SCORing Atopic Dermatitis; SQAAQ= subcutaneous administration assessment questionnaire; TCI = topical calcineurin inhibitors; TCS = topical corticosteroid.

For regulatory submissions, primary and major secondary endpoints will be adjusted for multiplicity. Details can be found in Section 6.2.

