#### **Flare**

Disease flares will be assessed based on rescue therapy usage; flare is defined as initiation or intensification of rescue therapy. A summary of the percentage of patients in the mITT Population rescued by week and a listing of patients in the ITT Population who use rescue medication will be provided.

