### **6.16.1. Impact of COVID-19**

Impact of pandemic (for example, COVID-19) on analyses may be addressed prior to study unblinding at Week 16 DBL, once the impact on study conducts are fully understood. In general, any missing assessments/visit window will be documented as protocol deviations. For patients who have missing assessments at Week 16 due to COVID-19, these patients may enter the escape arm. A summary or listing may be provided to summarize missing visits due to COVID-19.

Treatment discontinuation due to pandemic will be treated the same type of intercurrent event as treatment discontinuation due to reasons other than lack of efficacy. Strategies of how this type of intercurrent event will be handled are described in Section 6.2. Intermittent missing assessment due to pandemic will be treated the same as any other intermittent missing values. Details of how missing data will be handled are described in Section 6.4.

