### 2. Systemic Atopic Dermatitis Treatment (including systemic corticosteroids, immunosuppressant, biologics and phototherapy/photochemotherapy)

Route of systemic treatments administration includes: Oral, Intra-Arterial, Intramuscular, Intraperitoneal, Intravenous, Subcutaneous, and Transdermal. (This condition applies to the following categories except for phototherapies.)

Systemic Corticosteroids: ATC code is H02.

Immunosuppressant: Defined as: ATC2 is L04 or Preferred Terms (PTs) of Abrocitinib or Ruxolitinib.

Biologics: Defined as following PTs:

- Infliximab, Infliximabum, Etanercept, Etanerceptum, Adalimumab, Adalimumabum, Certolizumab, Certolizumabum, Certolizumab pegol, Golimumab, Golimumabum, Ozoralizumab, Afelimomab, Afelimomabum, Tumor Necrosis Factor Alpha (TNF-) Inhibitors, Tabalumab, Tregalizumab, Anakinra, Basiliximab, Basiliximabum, Daclizumab, Daclizumabum, Tocilizumab, Tocilizumabum, Mepolizumab, Mepolizumabum, Rilonacept, Rilonaceptum, Ustekinumab, Canakinumab, Briakinumab, Fezakinumab, Sirukumab, Sarilumab, Lebrikizumab, Secukinumab, Olokizumab, Gevokizumab, Brodalumab, Ladarixin, Ixekizumab, Dupilumab, Tildrakizumab, Tildrakizumabum, Reslizumab, Reslizumabum, Guselkumab, Guselkumabum, Olamkicept, Fletikumab, Bimekizumab, Mirikizumab, Risankizumab, Abatacept, Ligelizumab, Vedolizumab, Belimumab, Nemolizumab, Tralokinumab, Omalizumab

Phototherapy or Photochemotherapy:

If the programming search of the medication name (actual term or PT) contains 'photo,' then medical is to manually review to confirm whether the medication in question is indeed 'Phototherapy' or 'Photochemotherapy.'

---

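### Systemic corticosteroids given for non-skin adverse events are counted as AD rescue and AD flare, because the SAP's rescue definition has no indication condition

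*Protocol*

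**What the plan says.** Protocol 6.1 first deals with systemic corticosteroids given for AD, then adds a rule for the same drugs given for something else: "If used for treatment of AEs (for example, worsening of existing condition, such as asthma exacerbation), it will be treated as rescue medication", with a reference to Section 6.4. That section describes rescue as a means "to control intolerable AD symptoms".

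SAP 6.10.1 defines rescue for AD as high or ultra-high potency TCS, or any systemic agent in Appendix 2. Appendix 2 identifies the systemic agents by coding: "Systemic Corticosteroids: ATC code is H02", ATC class L04 plus two named drugs for immunosuppressants, and a list of preferred terms for biologics, with a filter on route. The only manual review is to confirm that a term containing 'photo' really is phototherapy.

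Under the Flare heading, SAP 6.10.1 states that "flare is defined as initiation or intensification of rescue therapy". It promises a weekly summary of the percentage rescued in the mITT Population and a listing of rescue users in the ITT Population. SAP Table KGAD.4.1 lists "Percentage of patients rescued by visit" among the other efficacy endpoints.

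The field needed to tell AD use from other use exists. Protocol Section 6 says of every medication: "Information on the dose, unit, frequency, route of administration, start date, discontinuation date, indication, and reason for use will be recorded".

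**The concern.** A reader will take a flare rate, or a percentage rescued, as a measure of AD control. As the rules are written, an oral steroid course for an asthma exacerbation adds one event to both, even in a patient whose skin is clear. The planned breakdown separates high-potency TCS from systemic therapy, but not AD use from other use, so no planned table shows how much of the count is unrelated to skin.

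The fault is narrow. Counting any systemic steroid as failure in the primary analysis is one decision. Using the same variable, unchanged, as an AD flare measure is another, and only the second is criticised here.

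**Working it through.** **Step 1: the chain in the text.**

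| Link | Source | Condition on indication? |
|---|---|---|
| Systemic steroid for an AE is rescue | Protocol 6.1 | No; AE use is expressly included |
| Systemic rescue found by code, term and route | SAP Appendix 2 | None written |
| Flare is rescue use | SAP 6.10.1 | None written |
| Percentage rescued is an efficacy endpoint | SAP Table KGAD.4.1 | None written |

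The Appendix 2 heading, which speaks of treatment for AD, might suggest AD-indicated use only. No filter follows it, and Protocol 6.1 says the opposite for steroids.

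**Step 2: the plan's own figure.** Protocol 9.12 and SAP 5.2 state power above 95% with 150 and 75 patients, a two-sided Fisher exact test and alpha 0.05. Exact enumeration gives 98.4% for IGA 0/1 (38% versus 13%) and 99.99% for EASI-75 (58% versus 20%). The statement reproduces.

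**Step 3: the flare and rescue summary.** The documents give no rates, so everything in this step is assumed. Let r be the AD-driven rescue rate and q the proportion given a systemic steroid for a non-AD reason, independent of r. Then

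- observed rate = r + (1 − r)q
- non-AD share of counted events = (observed − r) / observed

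Example for lebrikizumab, r = 5%, q = 2%: 0.05 + 0.95 × 0.02 = 0.069; share = 0.019 / 0.069 = 28%.

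With r = 5% on lebrikizumab and 15% on placebo, and q equal in both arms:

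| q | Lebrikizumab | Placebo | Difference (points) | Ratio | Non-AD share, lebrikizumab | Non-AD share, placebo |
|---|---|---|---|---|---|---|
| 0 | 5.00% | 15.00% | 10.0 | 0.33 | 0% | 0% |
| 1% | 5.95% | 15.85% | 9.9 | 0.38 | 16% | 5% |
| 2% | 6.90% | 16.70% | 9.8 | 0.41 | 28% | 10% |
| 5% | 9.75% | 19.25% | 9.5 | 0.51 | 49% | 22% |

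With r = 10% and 25%, the ratio moves from 0.40 to 0.42, 0.45 and 0.50 at the same three values of q. The absolute difference hardly moves, since it is only multiplied by (1 − q). The rates, their ratio and what the events mean change more. One misclassified patient adds 1/150 = 0.67 points on lebrikizumab or 1/75 = 1.33 points on placebo.

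**Step 4: the primary endpoint.** If response is independent of non-AD steroid use, the IGA 0/1 rate becomes p(1 − q), and with equal q the difference is 25 × (1 − q) points.

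- q = 1%: 37.62% − 12.87% = 24.75, a loss of 0.25 points
- q = 4%: 36.48% − 12.48% = 24.0, a loss of 1.0 point

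Fisher power is 98.1% at q = 2% and 97.7% at q = 5%. As a stress test, q confined to lebrikizumab gives 97.8% at 2%, 96.8% at 5% and 94.0% at 10%. It falls below the planned figure only at the last value.

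**The case against.** The strongest defence is that the rule is deliberate. Protocol 6.1 places systemic corticosteroids among therapies known to affect AD, so a course distorts later skin scores whatever its purpose. Protocol 9.1 names systemic corticosteroid use as a reason to set values to baseline, and SAP 6.2.1 asks about response achieved without rescue. This stands in full for the primary analysis. It does not justify calling the same course an AD flare.

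It also stands that the output is minor. The flare summary and the rescue endpoint appear to be one descriptive display. It has no row in SAP Table KGAD.6.9 and is outside both testing schemes. Non-AD systemic courses can fall only in the systemic line of the rescue summary, which bounds them. Exclusion 9 bars uncontrolled chronic disease likely to need bursts of oral steroids.

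Three stronger readings are tempting, and the documents do not support them.

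- *Flares go missing.* Protocol 6.3 says "If AD lesions return or a patient experiences a flare, TCS treatment may be resumed", and such an event is not a flare under the SAP. But low and mid-potency TCS/TCI use and diary data are summarised (SAP 6.10.1), TCS/TCI-free days and time to TCS/TCI-free use are endpoints, and AD exacerbation has its own adverse-event summary (SAP 6.14.6.8).
- *COVID-19 is handled inconsistently.* SAP 6.16.1 says "Treatment discontinuation due to pandemic will be treated the same type of intercurrent event" as stopping for reasons other than lack of efficacy. Stopping because of the pandemic and receiving a drug that acts on AD are different intercurrent events, and SAP 6.2 assigns strategies by event.
- *A drug effect on asthma could create a false rescue benefit.* Protocol 1.4 reports pooled pharmacokinetic data from asthma patients. Neither document reports an effect on exacerbations or on steroid use, so an imbalance between arms would be pure assumption.

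**Conclusion.** The point holds in a limited form. Followed as written, the plan counts systemic steroid courses given for non-AD adverse events as AD rescue and AD flare, and no planned summary separates them. The size cannot be determined from the documents. The 16 to 49% share of lebrikizumab flares and 5 to 22% of placebo flares rests on assumed AD rescue of 5% versus 15%, equal non-AD use of 1 to 5%, and independence. The true frequency is probably low given exclusion 9.

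A reader might infer that the primary result is compromised. It is not: equal non-AD use of 1 to 4%, again assumed, takes about 0.25 to 1.0 points off the IGA 0/1 difference, towards no effect, with power above 97%. No confirmatory error rate is affected. This is a correction to how one descriptive efficacy output is defined and labelled.

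**What to change.** Leave the primary estimand and its handling of rescue unchanged. In SAP 6.10.1:

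1. Report the flare and percentage-rescued summary by arm and by recorded indication, AD versus non-AD.
2. Base the flare definition on AD-indicated rescue only.
3. Show non-AD systemic corticosteroid or immunosuppressant use on a separate line.
4. State how Protocol 6.1, which counts AE use as rescue, is reconciled with Protocol 6.4, which ties rescue to AD symptoms, for this output. No clinical rule is proposed.

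The cost is SAP wording, one filter on a field already collected, and a treatment-blinded medical check of the indication entries. SAP Version 4 was written after the primary database lock, when a few study-team statisticians had been unblinded, so an addition made after unblinding should be labelled post hoc.

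An indication-based sensitivity analysis of IGA 0/1 and EASI-75 is optional. It would handle non-AD systemic agents as a treatment stop for reasons other than lack of efficacy, with multiple imputation, instead of setting values to baseline. On the figures above it would be expected to change little.

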6.2. Moisturizers

Non-medicated moisturizers are to be used during the study. The patient may continue her/his current over-the-counter moisturizer regimen, if approved by the Investigator.

6.3. Topical Treatment for Atopic Dermatitis

All patients will be instructed to use TCS for AD symptoms starting at the Baseline visit (Day 1).

Patients may taper or stop TCS use, as needed. If AD lesions return or a patient experiences a flare, TCS treatment may be resumed at the patient's discretion.

Low-potency TCS or topical calcineurin inhibitors (TCI) may be used for sensitive areas only, i.e., face, neck, intertriginous and genital areas.

A mid-potency TCS, triamcinolone acetonide 0.1% cream, and a low-potency TCS, hydrocortisone 1% cream (for use on sensitive skin areas) will be provided by the Sponsor or clinical site for use in this trial. Patients are to be instructed to return all used and unused TCS medication (tubes) to the study site for accountability purposes.

The Investigator must keep an accurate record of the number of tubes received, dispensed/used, and those returned to the Sponsor or designee. The Sponsor or designee will provide forms to facilitate inventory control. All accountability forms and treatment logs must be retained in the Investigator's permanent study file, and these records must be available for inspection at any time by the Sponsor, its designees, or by regulatory agencies.

The study monitor will perform accountability for all TCS tubes at the site, and will assist in returning all used, unused, and expired materials, to the Sponsor/designees, or destroy it according to the study site's standard operating procedure, if accepted by the Sponsor.

All TCS and TCI use will be recorded daily by the patient using an electronic diary.

6.4. Rescue Treatment for Atopic Dermatitis

The goal of this Phase 3 study is to demonstrate the efficacy and safety of lebrikizumab when used in combination with TCS for AD. However, add on rescue therapies may be needed, if the patient experiences clinical worsening of symptoms that are intolerable.

If medically necessary (i.e., to control intolerable AD symptoms), high potency TCS or systemic treatments (e.g., oral corticosteroids, phototherapy, cyclosporin, etc.) may be used. Study drug must be discontinued for patients receiving systemic rescue treatment. Patients should continue to attend all study visits and be assessed for safety and efficacy according to the schedule of events, even if rescue medication is initiated.

Patients using topical or systemic rescue medication who complete the study through Week 16 will be eligible to continue to a separate long-term extension study after the Week 16 visit has been completed.

All rescue treatment usage must be captured in the eCRF.

7. STUDY PROCEDURES

The required procedures for each study visit are outlined in [Appendix 1](#). The timing of each study day is relative to the day of initial dosing (Day 1, Baseline).

7.1. Screening Visit

The purpose of the screening visit/period is to ensure that appropriate patients are entered into the study and that they remain stable during the pre-treatment period.

- Obtain written informed consent/assent prior to performing any study procedures
- Review Inclusion/Exclusion Criteria
- Measure vital signs
- Review immunization record for adolescent patients
- Perform a complete physical examination, including height and weight
- Collect concomitant medication and procedure/therapy information
- Complete the following assessments: IGA, BSA, and EASI
- Draw blood samples for laboratory tests, including serum pregnancy
- Collect urine sample for urinalysis
- Complete medical history/review of systems
- Collect demographic information
- Instruct the patient to apply a moisturizer at least twice daily
- Assign eDiary and instruct the patient on the completion of the following assessments: Pruritus and Sleep-Loss (daily), and POEM (weekly). Instruct patient to record TCS/TCI use daily.

